The Society of American Gastrointestinal and Endoscopic Surgeons (SAGES) has devoted significant resources to the development of the Fundamentals of Endoscopic Surgery (FES) program. Much like the Fundamentals of Laparoscopic Surgery (FLS), FES consists of both a high-stakes didactic examination and a skills test. If the FES program follows a trajectory similar to that of FLS, it will be widely disseminated and may become a requirement for American Board of Surgery Certification ¹. Because of the high stakes associated with FES, it is necessary to develop a training program that would best prepare the learners for the skills examination, as well as provide a curriculum for skills remediation for those who are initially unsuccessful.

Based on the success of the previously developed FLS skills training curriculum²⁻⁵, we will develop a proficiency based skills curriculum using the low-cost, non computer based Simulated Colonoscopy Objective Performance Evaluation (S.C.O.P.E) platform. This will be done in 3 phases. In phase 1, experience endoscopists will define the performance goals that will be used in the curriculum. In phase 2, novice endoscopists will train on each of the S.C.O.P.E. tasks until they reach the performance goals. Their endoscopic skills will be assessed both before and after training with 3 different validated assessment tools, FES, S.C.O.P.E. and the Global Assessment of Gastrointestinal Endoscopic Skills for Colonoscopy (GAGES-C). Finally, for phase 3, the durability of skills acquisition will be evaluated with both 6 month and 12 month follow up for the novice endoscopists.

Background

The Society of American Gastrointestinal and Endoscopic Surgeons (SAGES) has devoted a significant amount of resources to the development of the Fundamentals of Endoscopic Surgery (FES) program¹. Much like the Fundamentals of Laparoscopic Surgery (FLS), FES consists of both a high-stakes didactic examination and a skills test. If the FES program follows a trajectory similar to that of FLS, it will be widely disseminated and may become a requirement for American Board of Surgery Certification in Surgery. Because of the high stakes associated with FES, it is necessary to develop a training program that would best prepare the learners for the skills examination, as well as provide a curriculum for skills remediation for those who are initially unsuccessful.

Proficiency based training has proven useful in preparing for FLS testing. In proficiency-based training, learners train to expert levels prior to high-stakes testing. Our group has been instrumental in the development of proficiency-based training for FLS. After completion of the proficiency based training program for FLS, learners have 100% certification pass rate. The skills acquisition was durable and learners were able to return to high levels of performance on simulators even after a lengthy hiatus from training²⁻⁵. An analogous proficiency-based training program for FES would likely demonstrate similar utility.

FES relies on a computer-based platform for skills testing. A commercially available virtual reality (VR) endoscopy simulator with software modifications will be used to administer the examination. VR simulators such as the one used for FES have several limitations: high maintenance costs, suboptimal durability, and difficulty mimicking the feel of performing live clinical cases. Furthermore, the start-up costs of the simulator used for FES range from \$40,000 to over \$100,000. Such costs will likely be prohibitive to many surgery training programs and simulation centers, therefore regional testing centers are being developed.

The SAGES FES Task Force, in collaboration with SAGES leadership, has opted not to allow practice on the specific FES tasks. Even those centers who own the VR simulator will only be able to access the FES skills for testing. Without access to the FES tasks, or tasks which closely mimic those in FES, learners may be inadequately prepared for taking the high-stakes exam.

We perceived a need for an affordable, non-computer based, assessment tool that can be used for training in basic flexible endoscopy. Our program, termed Simulated Colonoscopy Objective Performance Evaluation (SCOPE), uses a commercially available physical colonoscopy model and a standard colonoscope to perform four specific tasks: scope navigation, tool targeting, loop reduction, and mucosal inspection with retroflexion. The physical model has several distinct advantages over computer based models. Since a genuine colonoscope is used, the learners gain familiarity with the handling of the same instruments used in clinical. The physical model uses a rubber colon designed to mimic the feel of a true colon. The maintenance costs are low since

there are no computerized components of the model. In addition, the acquisition costs are affordable, with an initial investment of less than \$10,000 required to begin training.

Our preliminary data using the physical colonoscopy model and our SCOPE program have been encouraging. We have shown that SCOPE, based on the above four tasks, can be administered in less than 50 minutes per learner. We have identified the key metrics for incorporation into a scoring system and have accumulated validity evidence that the SCOPE scoring system objectively assesses the technical skills required to perform standard flexible endoscopy. For each of the four tasks, we have validity evidence that task scores reliably differentiate between novices, intermediates, and experts. Our data indicate that SCOPE is a reliable, simple program for simulating basic flexible endoscopy. SCOPE could be an ideal training platform to prepare for basic clinical endoscopy and FES testing.⁷⁻⁹

The goal of this proposal is to develop a proficiency based skills curriculum for FES using SCOPE. We will draw on the success of proficiency based training for FLS and apply the same methodologies to FES. A proficiency based skills curriculum for FES using SCOPE could help prepare learners for the FES examination and could foster the success of the entire FES program.

Hypothesis

Our hypothesis is that training to expert derived performance goals on a non-computer based flexible endoscopy simulator will allow a group of novice endoscopists to acquire a level of skill adequate to achieve a greater than 80% pass rate on the manual skills portion of the Fundamentals of Endoscopic Surgery (FES) assessment. After completing this proficiency based curriculum, these novice endoscopists will also demonstrate performance scores on the Global Assessment of Gastrointestinal Endoscopic Skills for Colonoscopy (GAGES- C) and Simulated Colonoscopy Objective Performance Evaluation (S.C.O.P.E.) assessments equivalent to intermediately experienced endoscopists (50 - 140 endoscopies). Finally, the group of novice endoscopists who complete this proficiency based curriculum will demonstrate significantly higher scores on FES, GAGES-C, and S.C.O.P.E when compared to a control group that simply undergoes repeat assessment without any formalized curriculum (to control for learning effect of repeated assessment).

Methods

Subjects: Two distinct categories of subjects will be needed:

Novice subjects (NS): 45 novice subjects will be recruited. (See power analysis) Inclusion criteria include any healthcare professional adult >18 years of age who has not had significant previous experience with a flexible endoscopic simulator and has performed less than 10 endoscopies (EGD and colonoscopy). Significant endoscopic simulator experienced is defined by self reported time on any endoscopic simulator of greater than 5 hours, or having previously completed a formalized endoscopy training curriculum. Professional backgrounds include but are not limited to medical students and resident physicians. Subjects will be recruited regardless of pregnancy status. Subject data will be identified in databases only by subject number. No identifying data will be recorded and performance will in no way affect any subjects course grading or evaluation on any rotation.

Experienced subjects (ES): 30 experienced subjects will be recruited (see power analysis) Inclusion criteria include any gastrointestinal healthcare professional adult >18 years of age who has performed more than 50 endoscopies. Professional backgrounds include and are limited to General Surgery PGY ≥4, Gastroenterology fellows, General, Colorectal, and Minimally Invasive Surgeons, and Gastroenterologists. Subjects will be recruited regardless of pregnancy status. Subject data will be identified in databases only by subject number. No identifying data will be recorded and performance will in no way affect any subjects grading or evaluation on any rotation, or credentialing.

Apparatus and Procedures:

Kyoto Colonoscopy Simulator: A non-computer based physical colonoscopy model manufactured by Kyoto Kagaku Co Ltd, Japan. A plastic external form contains a latex simulated colon that can be configured into different "cases" based on the standard inserts included. This model must be used in conjunction with a colonoscope with capabilities for insufflation, irrigation, and suction, connected to an imaging system and displayed on a 4:3 aspect ratio video monitor.

GAGES-C Assessment: for this assessment, subjects will perform a simulated colonoscopy on the Kyoto simulator. This will involve navigating to the cecum on a standardized case, followed by withdrawal and mucosal inspection to identify 5 numbered targets. For 3 of the targets, subjects will be asked to make contact with them using a standard biopsy forceps. External views of the endoscope and the subjects hands will be video recorded along with the endoscopic view combined into one screen using a video mixer. The recordings will then be scored using GAGES-C scoring system, which assesses scope navigation, use of strategies (loop reduction, positioning, etc), ability to keep a clear field, instrumentation (facility using tools) and quality of exam each on a anchored 5pt likert scale⁶. Evaluators using the scoring system will be blinded to the subjects group and training status.

Simulated Colonoscopy Objective Performance Evaluation (S.C.O.P.E): This is based on the framework of the Kyoto platform described above but has been modified into 4 separate tasks

that include performance metrics and a scoring system. The tasks include *Scope Manipulation*: requires use of torque and tip deflection to move a shape in the colon to the 6 o'clock position and align that shape within an outline of the shape placed upon the monitor screen. Alignment must be held for 5 seconds for each shape before continuing to the next shape. The modified colon contains 10 shapes in various locations. *Tool Targeting*: requires coordination with biopsy forceps to contact a metal target, completing a circuit and sounding a tone. Contact must be maintained for 5 seconds on each target before continuing to the next. The modified colon segment contains 10 targets in various locations. *Loop Management*: perform scope navigation to correctly manage the formation of a standard alpha loop. The task is to insert the scope in the simulated rectum followed by navigation to the cecum through a redundant sigmoid. If a loop is formed, it must first be recognized and then successfully reduced to continue advancing the colonoscope. The task will begin in the left lateral decubitus position but on request, the task can be repositioned in the supine, prone, or right lateral decubitus position. Additionally, abdominal pressure can be provided by the proctor where and when directed by the subject. *Mucosal Inspection*: during withdraw of the colonoscope, identification of polyps placed randomly throughout a length of simulated colon and rectum requiring careful mucosal inspection, including retroflexion.

As an assessment, the tasks are administered sequentially by a proctor using a standard instruction script and standardized scoring metrics. As a training tool, subjects will train on each task until a defined expert performance proficiency level is reached.

Fundamentals of Endoscopic Surgery (FES): The manual skills portion of the FES program is based in virtual reality and delivered by either the GI Mentor II or Bronch Mentor simulators (Simbionix USA, Cleveland OH). It consists of 5 task that assess scope navigation, tool manipulation, loop reduction, retroflexion, and mucosal inspection. The exam is completely computer based and is administered by a proctor. All task instructions and scoring are completed by the computer based simulator and uploaded to a network server. The FES exam can only be given at FES test centers.

Methods:

Phase I: *Establishing performance goals and references*- This phase will involve the ES group to define the task specific training goals for the novice curriculum. Each ES subject will complete a GAGES-C assessment followed by 3 trials of each of the S.C.O.P.E tasks. Three trials are used to help ensure that the simulator specific learning curve has been accounted for. The GAGES-C scores will be used to help calibrate performance of experienced endoscopist on the Kyoto model as the GAGES-C data to date has come from actual colonoscopies. The mean trial 3 performance on each of the S.C.O.P.E. tasks will be used to set the proficiency levels for the training curriculum to be utilized in Phase II.

Phase II: *Assessing the effects of the curriculum*- The NS group will be randomized in a 2:1 ratio between the training group (NST) and the control group (NSC) respectively. Both groups will undergo a pretest consisting of a GAGES-C assessment, a S.C.O.P.E assessment, and an FES assessment. Subjects in the NST group will then train to the proficiency levels established in Phase I for each of the S.C.O.P.E. tasks. The NST group will then undergo a posttest

[figure not shown]
consisting of a GAGES-C assessment, S.C.O.P.E assessment, and FES assessment within 2 weeks of completion of the curriculum. NSC subjects will receive no training during this phase and will return for the posttest after the same amount of time as it took for the NST group to complete their training. Both groups will be queried as to any additional clinical endoscopic experience that they received between the pretest and the posttest. Once the NSC subjects complete the posttest, they will be allowed to complete the curriculum if they wish, including an additional post curriculum assessment within 2 weeks of curriculum completion.

Phase III: Long term follow up- All subjects who complete the curriculum in both the NST and NSC groups will be asked to return for additional assessment at 6 months and 12 months. Subjects will be queried as to any additional clinical endoscopic experience that they received between the assessments. This follow up assessment will consist of 3 trials of each S.C.O.P.E. task to evaluate for rapid spontaneous recovery of skills seen in previous similar studies.³ They will also undergo an FES assessment.

Data Analysis: For continuous variables, mean performance differences between pretest and posttest assessment within groups will be statistically assessed for significance using paired t-test. Mean performance differences between groups will be statistically assessed for significance with unpaired t-tests. Differences for multiple repeated measures during long term follow up will be assessed with repeated measure ANOVA. For proportions, rates of achieving a passing score on the FES assessment will be statistically assessed for significance using Fishers exact test or chi squared as appropriate.

Sample Size / Power Analysis

Samples size can be estimated using previous data for two of our primary endpoints stated in the hypothesis, GAGES-C and S.C.O.P.E. Previously published GAGES-C scores for novice and intermediate endoscopists⁶ showed a difference in means between the two groups of approximately 6, with a standard deviation in the novice group of 3.8 and intermediate group of 1.6. If we use a paired, two tailed t-test (since our subjects undergo a pre-test then a post-test) with alpha set at 0.05, estimated standard deviation of 5.5 and a power of 80%, then we need 9 subject to be able to reject the null hypothesis. Since the exact difference in performance improvement is unknown, Figure 1 shows sample size and power for a difference in means ranging from 3 to 6.

Similar calculations can be done using the S.C.O.P.E. score endpoint. Unpublished data currently undergoing peer review showed that for S.C.O.P.E score, novice and intermediate

endoscopists showed a difference in means between the two groups of approximately 115 with a standard deviation in the novice group of 94 and intermediate group of 62.⁹ If we apply the same paired, two tailed t-test with alpha set at 0.05, estimated standard deviation of 150 and a power of 80%, then we need 15 subject to be able to reject the null hypothesis. Since the exact difference in performance improvement is unknown, the graph below shows sample size and power for a difference in means ranging from 95 to 125.

[figure not shown]

Figure 2: Required sample size as a function of statistical power for differences in means between groups ranging from 95 - 125

Based on these evidence based estimates, a sample size of 24 experimental subjects would allow us to be well powered across a broad range of differences in mean performance. If we allow for a 20% drop out rate, since participation is completely voluntary, that would result in recruiting 30 novice experimental subjects. or 10 subjects / site. In a separate analysis conducted similar to the ones above (not shown), approximately 12 control subjects would be required to reject the null hypothesis between the experimental and control groups with an 80% power. Applying the 20% drop out rate to the control group brings the target subject recruitment to 15, or 5 / site.

Comparison of the ES group with other groups is not part of our hypothesis testing, as this group serves to establish the reference criteria for the GAGES assessment and the proficiency scores for S.C.O.P.E. An estimated recruitment of up to 10 subjects per site should be more than adequate to ensure a broad representation of the desired skill set.

SAGES RESEARCH GRANT APPLICATION BUDGET SHEET

09BudgetSheet

Detailed budget for 12 month period from __ Jul. 1, 2013 through Jun. 30, 2014.

Dollar amount requested (Omit cents) _____ 30,000

Total for the grant request may not exceed \$30,000.

* Salary funds should be used for staff required to execute the study, but should not be used for salary support for the primary investigator. If salary support exceeds 50% of the project budget, then specific justification is required.

**Funds requests for travel for the presentation of a SAGES funded study should be limited to \$1,000.

NAME	POSITION TITLE	TIME/EFFORT		SALARY	FRINGE BENEFITS	SUB-TOTALS
		%	Hrs/ Week			
1. [name]	Principal Investigator*	5	2			
2. [name]	Assoc. Investigator	4	1.5			0
3. [name]	Assoc. Investigator	4	1.5			0
CONSULTANT COSTS						
EQUIPMENT						
(List all Items&Total Equipment Cost)		Items				Subtotal
SUPPLIES						
(List all Items&Total Supplies Cost)		Items Kyoto Colonoscopy SCOPE Models (6 at \$2,500 each, total \$15,000), Colon Inserts (6 at \$1,000 each, total \$6,000), MacBook pro computer 13 inch (3 at \$1,300 each, total \$3,900), Mac Software \$660, Misc recording / simulator maintenance supplies \$190				25,750
TRAVEL**						
(List all Items & Total Cost)		PI site visit travel to Tulane and UMD two visits each \$3,250, SAGES meeting travel for presentation - \$1000				4,250
PATIENT CARE COSTS						
CONSORTIUM/CONTRACTUAL COSTS						
OTHER EXPENSES						
(List all Items & Total Cost)		Items				Subtotal
TOTAL DIRECT COSTS						30,000

Budget Justification

Personnel

E. [name] (5% Effort), Principal Investigator. [name] will lead the research effort. He will oversee the resident researchers and Associate-Investigators. He will submit the protocol to and be the lead contact for the IRB, which will allow the residents enrolled in the courses to take a skills test. Finally, he will present his findings at the SAGES meeting. Since his salary is paid for by the US Air Force, no salary support is requested.

[name] (4% Effort), Associate Investigator from Collaborating Organization. [name] will lead the research effort at Tulane. He will oversee the residents and fellows' work there and report results to the PI, [name]. No salary support is requested.

[name] (4% Effort), Associate Investigator from Collaborating Organization. [name] will lead the research effort at the University of Maryland, School of Medicine. He will oversee the residents and fellows' work there and report results to the PI, [name]. No salary support is requested.

Equipment \$0

Supplies \$25,750

\$15,000 is requested for Kyoto colonoscopy SCOPE models (6 at \$2,500 each), which mimic real human tissues, and the residents and fellows will use to practice their techniques on them hands on. \$6,000 is requested for colon Inserts (6 at \$1,000 each) to be placed inside the Kyoto colonoscopy SCOPE models (above) so that students can practice their techniques on them. \$3,900 is requested for MacBook pro computers 13 inch (3 at \$1,300 each) so that student scope images and skills test results can be captured at each of the three worksites, maintain and organize data and protocol documents, communicate among the sites, and organize skills test documents and materials. \$660 is requested for Mac Software to record images and for basic word processing and spreadsheet applications. \$190 is requested for miscellaneous recording / simulator maintenance supplies to maintain the camera equipment and keep the simulator models in good working condition.

Travel \$4,250

\$1,000 is requested for travel to the SAGES meeting for the PI to present the results of the project. \$3,250 is requested for two site trips (each) to the University of Maryland in Baltimore, MD and to Tulane University in New Orleans, Louisiana for the PI to meet with the Associate-Investigators to exchange ideas and discuss the progress of the project.

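### No posttest is scheduled for training-arm subjects who do not finish the curriculum, so the completer-versus-control comparison would favour training if non-completion is related to ability

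*Protocol*

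**What the plan says.** Novices are randomised: "The NS group will be randomized in a 2:1 ratio between the training group (NST) and the control group (NSC) respectively". Both arms take a pretest on GAGES-C, S.C.O.P.E. and FES.

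**Training arm (NST).** The S.C.O.P.E. description under Apparatus and Procedures says that "subjects will train on each task until a defined expert performance proficiency level is reached". Phase I defines that level: "The mean trial 3 performance on each of the S.C.O.P.E. tasks will be used to set the proficiency levels for the training curriculum". Phase II then sets the three-part posttest, ending with the "FES assessment within 2 weeks of completion of the curriculum". It gives no time limit, no cap on attempts and no alternative posttest for someone who stalls or stops.

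**Control arm (NSC).** Controls receive no training and return after the time the training group took. No performance condition applies to them.

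**Comparison.** The Hypothesis section sets trained novices who finish the curriculum against controls. On the training side it predicts that "the group of novice endoscopists who complete this proficiency based curriculum will demonstrate significantly higher scores on FES, GAGES-C, and S.C.O.P.E". For the other side it names no completion requirement; the scores are to be higher "when compared to a control group that simply undergoes repeat assessment without any formalized curriculum". It also predicts that training to the expert-derived goals will let novices "achieve a greater than 80% pass rate on the manual skills portion of the Fundamentals of Endoscopic Surgery (FES) assessment". Phase III follows only those who complete the curriculum.

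**Expected loss.** Sample Size / Power Analysis plans for it: "If we allow for a 20% drop out rate, since participation is completely voluntary". The same 20% is applied to both arms.

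**The concern.** The between-group claim is the only part of the hypothesis that uses randomisation. Randomisation makes the two arms comparable when they are formed. Phase II then admits trained subjects to the posttest only after they have met a performance standard, and asks nothing similar of controls. For S.C.O.P.E. the filter uses the same tasks as the outcome.

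Ability-related loss is plausible, though not established. Novices have done fewer than 10 endoscopies and must reach an experienced-group mean on each of four tasks. The appended S.C.O.P.E. abstract reports mean total scores of 218 for novices (there 0 to 50 colonoscopies), 334 for intermediates and 395 for experts, a gap of 116 to 177 points. Participation is voluntary, so a slow learner can simply leave.

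At stake are the training-versus-control difference on all three measures and the reading of the FES pass rate. The fault lies in data collection: an analysis plan can define who is analysed, but it cannot supply posttest scores from people who were never tested.

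**Working it through.** **1. Planned loss (Sample Size / Power Analysis).** Recruited = evaluable / (1 − dropout).
- Training: 24 / 0.8 = 30, as stated, so 6 are expected to be lost.
- Control: 12 / 0.8 = 15, as stated, so 3 are expected to be lost.

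The protocol gives no separate rate for failing to reach proficiency.

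**2. Score shift if the losses are the least able.** This rests on assumptions that are not in the documents: the lost 20% are the lowest on a trait correlated ρ with the posttest score, scores are normal, training has no true effect, and control loss is random.

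Shift in SD units = ρ × φ(z₀.₂) / 0.8, with z₀.₂ = −0.8416 and φ = 0.280, so shift = 0.350ρ.

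| ρ | Shift (SD) | GAGES-C points (novice SD 3.8) | S.C.O.P.E. points (novice SD 94) |
|---|---|---|---|
| 0 | 0 | 0 | 0 |
| 0.3 | 0.10 | 0.4 | 10 |
| 0.5 | 0.17 | 0.7 | 16 |
| 0.7 | 0.24 | 0.9 | 23 |

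The SDs are those quoted in the power section. Against the 115-point S.C.O.P.E. difference used there, 16 and 23 points are 14% and 20%.

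**3. Type I error of the planned unpaired t-test.** Simulation with no true effect, 24 retained of 30 against 12 unselected controls, two-sided 5%, 40,000 runs per row. The losses not related to ability are taken at random.

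| Of the 6 losses, number lowest in ability | ρ | Shift (SD) | Type I error |
|---|---|---|---|
| 6 | 0.5 | 0.17 | 8.7% |
| 6 | 0.7 | 0.24 | 12.2% |
| 3 | 0.5 | 0.09 | 6.2% |
| 3 | 0.7 | 0.13 | 7.6% |
| 1 | 0.5 | 0.04 | 5.2% |
| 1 | 0.7 | 0.05 | 5.5% |
| 0 | either | 0.00 | 5% |

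Repeated runs of the two worst-case rows gave 8.2% to 8.7% and 12.2% to 12.4%. If controls also lost their lowest 20%, the mean shift would be close to zero.

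**4. FES pass rate under two denominators.** With 24 tested of 30 assigned, the rate among all assigned lies between (passes)/30 if none of the 6 untested would pass and (passes + 6)/30 if all would.
- 20 of 24 pass: 83.3% of completers; 20/30 = 66.7% to 26/30 = 86.7% of those assigned.
- 24 of 24 pass: 100% of completers; 24/30 = 80.0% to 30/30 = 100% of those assigned.

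**The case against.** The strongest reply has four parts.

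**Bias is not shown.** A reader might infer that slow learners disappear and that the results are therefore biased upward. The protocol does not say so. Training runs until the goal is met, so a slow learner may simply continue. The only reason given for dropout is that participation is voluntary, and the same 20% is applied to controls. This stands: direction and size are conditional on who fails to finish.

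**Controls are not all retained.** It is tempting to say that completers are compared with every control. The plan expects 12 evaluable of 15. This also stands. The asymmetry that remains is that a control's posttest does not depend on reaching a score.

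**The pass-rate claim is about completers.** A reader might take 24/30 = 80.0% to mean that the target of more than 80% cannot be met. That result comes from counting every untested subject as a failure, which is not the protocol's rule. The hypothesis concerns novices who trained to the goals, and the FLS precedent in the Background is framed in the same way. The completer rate is not an error.

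**Some of this belongs in an analysis plan.** Analysis sets and missing-data rules may be in a plan that is not shown, and the pretests could support sensitivity analyses. That does not remove the point. Phase II still provides no posttest for non-completers, and the Hypothesis section itself names completers as the group compared.

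**Conclusion.** The point holds in conditional form. As written, one randomised arm is filtered on performance after randomisation and the other is not, and trained subjects outside the filter have no outcome. The comparison favours training if non-completion is related to ability.

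A shift of about 0.17 to 0.25 SD with type I error of about 8% to 12% is an illustration at the unfavourable end for loss of this kind. It requires all 6 planned losses to be the least able, assumed correlations of 0.5 to 0.7, and random control loss. With 3 of the 6 related to ability, type I error is about 6% to 8%. With none, there is no score bias.

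The completer FES pass rate answers how people who reach proficiency perform. It does not answer what assigning novices to the curriculum achieves, for which 20/24 leaves a range of 67% to 87%. Both are worth reporting, and neither replaces the other.

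**What to change.** 1. **Phase II.** Schedule the posttest for every randomised NST subject who is willing to return, whatever their curriculum status, no later than a pre-set date. Set the control posttest to match, since it is now tied to the training group's completion time. The date limits when the test is taken; it need not end training for someone who wishes to continue.
2. **Hypothesis and Data Analysis.** Make the primary NST-versus-NSC comparison on all randomised subjects as assigned. Label the completer-versus-control comparison secondary.
3. **Reporting.** Give the proportion of NST subjects reaching proficiency. Give the FES pass rate for completers and for all assigned, counting untested subjects as not passing and describing that figure as a conservative bound.

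**Cost.** A few posttest sessions within the 30 already planned for recruitment, the choice of a latest date, and changes of wording. The headline estimate may be somewhat less favourable. Subjects who leave and will not return stay untested, so the change reduces the problem but does not remove it.

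### The sample size plans 10 training and 5 control novices at each of three sites, but neither the 2:1 randomisation nor the between-arm tests use site, so the split is not secured and some precision is lost

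*Protocol*

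**What the plan says.** **Sites and targets.** The Budget Justification refers to results "captured at each of the three worksites". Under Subjects, "45 novice subjects will be recruited". Sample Size / Power Analysis states that "a sample size of 24 experimental subjects would allow us to be well powered" and, after 20% dropout, "that would result in recruiting 30 novice experimental subjects. or 10 subjects / site". For controls, about 12 evaluable subjects are said to give 80% power between the arms, and the same dropout allowance "brings the target subject recruitment to 15, or 5 / site".

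**Allocation.** Methods, Phase II: "The NS group will be randomized in a 2:1 ratio between the training group (NST) and the control group (NSC) respectively". No site factor, blocking or type of list is given.

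**Analysis.** Data Analysis: "Mean performance differences between groups will be statistically assessed for significance with unpaired t-tests". FES pass rates are compared by Fisher's exact or chi-squared test. No site term appears in either.

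**FES hardware.** Apparatus and Procedures says the manual skills part of the FES program is "delivered by either the GI Mentor II or Bronch Mentor simulators". Available Resources lists a Bronch Mentor at the lead site and another at the second site. The third site's equipment is not in the text at hand.

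**The concern.** The sample size section sets arm targets site by site, and the stated allocation rule does nothing to deliver them. Sites can plausibly differ in score level. S.C.O.P.E. and FES are both administered by a proctor, and in the Loop Management task the proctor also applies abdominal pressure when the subject directs it. If sites differ and the arms are unevenly spread over them, part of the site difference falls into the arm comparison. Even with an even spread, site variance left in the error term costs power. With 30 v 15 randomised and 24 v 12 expected to be evaluable, there is little to spare. The matter cannot be left wholly to a statistical analysis plan: a site term can be added later, but an allocation already made cannot be redone.

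**Working it through.** **1. The plan's own targets.** Evaluable numbers divided by (1 − 0.20): 24/0.8 = 30 and 12/0.8 = 15. Over three sites: 30/3 = 10 and 15/3 = 5. Total 30 + 15 = 45. These reproduce, and imply 15 novices per site.

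**2. Chance of 10:5 at every site if allocation ignores site** (assuming exactly 15 recruits per site).

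- List fixed at 30:15 overall: C(15,5)³ / C(45,15) = 3003³ / 344,867,425,584 = 27,081,081,027 / 344,867,425,584 = 7.9%.
- Simple randomisation, each subject 2:1 independently: P(5 controls of 15) = 0.2143 per site, and 0.2143³ = 1.0% for all three.

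**3. How far off the split could be, fixed list.** Summing the same hypergeometric probabilities over all splits:

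| Event | Probability |
|---|---|
| at least one site off by 2 or more | 56% |
| at least one site off by 3 or more (2 or fewer, or 8 or more, controls of 15) | 21% |

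The central 95% range for one site is 7 to 13 training subjects of 15.

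**4. What a site term could gain.** The document gives no between-site variance, so the share R² of posttest variance explained by site is an assumption, with range 5% to 20%. The inputs behind the 12 controls are not shown, so the stated 80% is taken as the start. At 24 v 12, two-sided 0.05, 80% power corresponds to an effect of d = 1.02 SD (34 degrees of freedom). With site in the model and the arms balanced within site, the noncentrality is

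d / [√(1 − R²) × √(1/24 + 1/12)], on 32 degrees of freedom.

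| R² | Noncentrality | Power |
|---|---|---|
| 0.05 | 2.96 | 81.8% |
| 0.10 | 3.04 | 83.8% |
| 0.20 | 3.22 | 87.8% |

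**5. Cross-check by simulation** (10,000 runs per setting, 24 v 12, effect about 1.02 within-site SD). One of three equal sites is shifted by an assumed 0.5 or 1.0 within-site SD. The site variance is shift² × (1/3)(2/3), which is 0.056 or 0.222, so the shares are 0.056/1.056 = 5% and 0.222/1.222 = 18%.

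| Shift | Unstratified, unadjusted | Unstratified, adjusted | Stratified, adjusted |
|---|---|---|---|
| 0 | 79% | 77% | 79% |
| 0.5 SD | 77% | 77% | 79% |
| 1.0 SD | 71% | 77% | 79% |

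Here the within-site SD is held fixed and site adds variance, so the result reads as a loss from about 80%. In step 4 the total SD is held fixed, so it reads as a gain above 80%. The sizes agree: 2 to 3 points at the low end and about 8 at the high end. With no true effect, the planned unadjusted test rejected in 5.0% to 5.2% of runs, and the mean estimate was on target in every setting.

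**The case against.** **No contradiction, only silence.** A 2:1 ratio overall and 10:5 per site are compatible, and the latter can be read as 2:1 within site. Block and stratification details often sit in a separate plan. This stands to the extent that Phase II does not say site is ignored, so the probabilities above are conditional on that. But Phase II describes the allocation of the novice group as a whole, and the named between-arm tests are unadjusted.

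**Nothing depends on an exact 10:5 split.** True: no per-site analysis is planned and the per-site figures are recruitment targets. The 8% shows that the split is not secured. It does not measure harm, which is the power figure.

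**Site effects are held down by design.** S.C.O.P.E. uses a standard script and standard metrics, the GAGES-C colonoscopy rating uses a standardised case scored from video by blinded evaluators, and FES is instructed and scored by computer. This stands and argues for the lower end of the assumed range. If the between-arm t-test is applied to change scores, additive site shifts largely cancel. Data Analysis does not say so for that comparison, and an FES pass or fail result has no change score.

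**Two stronger readings a reader might infer.** One is that site differences bias the arm comparison. Under randomisation they do not: the estimate stays unbiased and the type I error stays near 5%. The other is that FES results will mix two simulators. The sentence on simulators describes the FES program in general, and the only FES machines listed for this trial's sites are Bronch Mentors. The third site's equipment is not visible, and that is no fault of the plan.

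**Conclusion.** The point holds as one of design efficiency. The protocol plans 10:5 at each of three sites, states an allocation that does not secure it, and names between-arm tests that do not use site. If allocation ignores site and 15 are recruited at each, the planned split is reached everywhere with probability about 8% or 1%, depending on the type of list. The cost is chance imbalance and lost precision. Its size rests on an assumed site share of 5% to 20% of posttest variance, for which power moves from 80% to about 82% to 88%, and is smaller for change scores. The unadjusted tests remain valid. A platform difference in FES is possible but not shown, and the conclusion does not rely on it.

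**What to change.** - **Methods, Phase II:** randomise 2:1 within each site, using concealed permuted blocks of varying size in multiples of 3. With 15 recruits per site and complete blocks this gives the 10:5 already planned.
- **Data Analysis:** include site as a fixed factor in the between-arm comparison of continuous scores, and use a site-stratified exact test (exact Cochran-Mantel-Haenszel) for posttest FES pass rates.
- **FES section, only if both simulator types turn out to be in use:** keep each subject on one type across all FES sittings, and record the type.

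The cost is a few sentences and 2 degrees of freedom, with no extra subjects or procedures. The two main changes belong together: in the simulation with no site difference, adjusting after unstratified allocation lost about 2 points of power (79% to 77%), while adjusting after stratified allocation lost almost none. Blocks at a site of 15 make some late allocations guessable. Varying and concealing the block size reduces this but does not remove it.
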